10.2 Variables

Overall survival (OS):

OS will be measured as the number of months from enrollment until death. Patients who are alive at the time of database lock will be censored on the date of last contact.

Progression-free survival (PFS):

PFS will be measured as the number of months from enrollment until progression or death, whichever comes first. Patients who are alive and free of progression at their last response evaluation will be censored on that date. Progression will be defined by the standards set forth within PCWG2.

Demographic variables:

Age at enrollment, race, ethnicity, ECOG status, extent of bone disease (< 6, 6-20, >20)

PD Effects:

Tumor/osteoblast/osteoclast, Ki-67, gamma H2AX, cleaved PRP, cytokeratin/PSA, BALP, and TRAP

Serum biomarkers:

ALP, BALP, APG, RANKL, OPN, OC, CTX, PINP

Bone marrow biomarkers:

Alkaline phosphatase, osteocalcin, DMP, sclerostin, tenascin, periostin, lumican, decorin, osteopontin, osteonectin, nidogen-1, TGFb-induced protein ig-h3.

10.3 Descriptive Statistics

Patient demographics and medical status at study enrollment will be tabulated for all enrolled patients. Descriptive plots and summaries of adverse events (AE), PD measures, as well as

serum and bone marrow biomarkers will be presented. The proportions of patients with at least a 30% increase or decrease in any marker will be presented. AEs will be reported by grade and relationship to study interventions (therapy and blood draws and biopsies all constitute study interventions).

10.4 Markers

Markers will be measured repeatedly over time. Any patient with both baseline and at least 1 later measurement will be included in descriptions of each marker. Patients will also be classified for each marker based on whether the marker decreased by at least 30%, stayed with 30% of baseline, or increased by at least 30%. Currently there is no knowledge of how the planned PD, serum, and bone marrow markers may predict overall survival. Exploratory analyses described below will be performed on the continuous values of the markers, changes, in the markers as continuous measures, and the classification strategy described here.

16.3.3 Survival Analysis.

Overall (OS) and progression-free (PFS) survival will be calculated from the date of study enrollment and will include all enrolled patients. Survival analyses will be performed when 90% of patients have died or 2 years after the last patient has completed treatment, whichever comes first. Plots of all patients and subgroups identified by marker exploration (described below) will be presented using the methods of Kaplan and Meier.

10.5 Primary Objective Exploration

Each marker will be tested individually using a Cox regression model to determine whether it is associated with overall survival. Markers measured on a continuous or ordinal scale will be included with their original units in the model. First, the baseline values will be used to determine if the baseline is associated with survival. Next we will calculate the percent change from baseline and use that as a continuous measure in the model. The ordered category of reduced by 30%, same, or increased by 30% grouping will be used in the model. Finally, all observed values of the marker will be included as a time-varying covariate in the Cox regression model. Since this is an observational study to identify potential usefulness of biomarkers in predicting overall survival, no formal adjustments for multiple testing will be needed for future trial planning. However, for publication, only markers with a significance level of ≤ 0.002 will be considered meaningful in predicting survival. This is based on a Bonferroni correction of approximately 25 markers of interest. Additional regression-tree style partitioning may be performed to identify potentially meaningful cutpoints for combinations of markers. Cutpoints will be examined together with demographic and medical status variables. This will be purely exploratory and will need to be confirmed in an independent data set in a future trial.

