The Investigator should delay cytotoxic chemotherapy, other systemic radioisotope, hemibody external radiotherapy or other investigational drug until the follow-up period. If such treatments have to be given during the treatment period, further study drug administrations must be discontinued. Patients with disease progression may continue treatment at the Investigator's discretion.

Myelosuppression:

Treatment-related changes in hematology parameters may occur.

- If a patient experiences CTCAE v4.03 Grade 3 or 4 neutropenia, thrombocytopenia, or anemia the administration of study drug should be delayed until recovery to Grade 2 or better.
- If a patient experiences CTCAE v4.03 Grade 3 or 4 neutropenia, thrombocytopenia, or anemia lasting > 14 days, further study drug administrations must be discontinued.
- Blood transfusion is acceptable between study drug administrations but not prior to the start of the study. Use of biologic response modifiers, such as G-CSF or GM-CSF, is allowed in the management of acute toxicity.

Gastrointestinal events:

Diarrhea should be treated as per local practice. A further dose of study medication should not be given before diarrhea is recovered to CTCAE v4.03 Grade 2 or baseline levels.

Nausea or vomiting should be treated as per local practice. A further dose of study medication should not be given before nausea or vomiting is recovered to CTCAE v.4.03 Grade 2 or baseline levels.

Spinal Cord Compression:

If the patient experiences spinal cord compression during the treatment period, the patient should be treated for the event, and may receive further study drug administration if adequately recovered.

Surgical Intervention:

If surgery is required, the patient should continue with study treatment, if this is considered safe in the treating Investigator's opinion. The surgeon needs to be notified that the patient has been given radioactive drug, and needs to follow the guidelines for radioactive protection.

Non-pathological fractures:

For traumatic fractures in weight-bearing bones during treatment phase, the study drug administration should be delayed for 2-4 weeks from the time of fracture.

Pathological fractures:

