10.6 Secondary Objective Analyses

Similar analyses as described for the primary objective will be carried out for progression-free survival as well. Graphical displays including individual biomarkers and progression events will be explored for patterns.

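### In the PFS repeats of the percent-change and ±30% marker models, nothing stops a change sampled at or after progression from being used to explain that progression

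*Combined protocol and SAP*

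**What the plan says.** Section 10.5 of the combined protocol and SAP plans four Cox models per marker for OS: baseline value, percent change, an ordered ±30% category, and all observed values as a time-varying covariate. On the second it says "Next we will calculate the percent change from baseline and use that as a continuous measure in the model". Only the fourth is called time-varying, so the natural reading of the second and third is one fixed value per patient. Section 10.6 then says "Similar analyses as described for the primary objective will be carried out for progression-free survival as well" and adds "Graphical displays including individual biomarkers and progression events will be explored for patterns".

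On the clock, Section 10.2 says "PFS will be measured as the number of months from enrollment until progression or death, whichever comes first" and, for censoring, "Patients who are alive and free of progression at their last response evaluation will be censored on that date". The survival-analysis paragraph (numbered 16.3.3, inside Section 10.4) says "Overall (OS) and progression-free (PFS) survival will be calculated from the date of study enrollment and will include all enrolled patients".

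On who is sampled after progression, Section 6 says "Patients with disease progression may continue treatment at the Investigator's discretion". It limits this where chemotherapy, another systemic radioisotope, hemibody radiotherapy or another investigational drug is needed: "If such treatments have to be given during the treatment period, further study drug administrations must be discontinued". Section 9 does not list progression as a reason for withdrawal. Section 10.1 counts a patient as evaluable with a baseline value and any one later sample.

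On timing, Section 3 plans the plasma panel at baseline and weeks 12, 16 and 24, and marrow cores before treatment and at weeks 12 and 24. The Section 7.2 table has marrow at screening, week 12 and week 24, but correlative blood and urine only at screening and week 24. Neither section ties a sampling time to a model.

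**The concern.** Take a patient who progresses at week 8, stays on treatment and is sampled at week 12. The PFS event is at week 8, yet the model explains it with a value that did not exist until four weeks later. If progression itself moves the marker, early progressors carry the moved values and the marker appears to predict PFS when it only follows it.

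This matters because Section 3 looks for early predictors of response and Section 10.8 says the findings will shape future trials. A follower is the wrong marker to carry forward. The 0.002 publication threshold in Section 10.5 deals with multiplicity, not with time order. It is written for survival, and the plan does not say whether it also applies to PFS.

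**Working it through.** **1. The plan's own figure.** Section 10.8 gives a detectable hazard ratio (HR) of 1.57 with 25 patients, SD 1.25, 80% power and two-sided 5%. With D = (1.960 + 0.842)² / (SD² × ln(HR)²), D = 7.85 / (1.5625 × 0.2035) = 24.7. For SD 1.5 and HR 1.45, D = 25.3. Both agree with 25, provided all 25 patients have the event. Per SD, the first figure is 1.57^1.25 = 1.76.

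**2. How many have progressed by the sample.** The documents give no PFS median. Assume exponential PFS with median m of 3, 5 or 7.4 months. The 7.4 is the ALP-progression median quoted in Section 1.4, used only as an assumed upper value. Week 12 is 2.76 months, and the share progressed is 1 − 2^(−2.76/m).

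| Assumed m (months) | Share progressed by week 12 | Of 25 | Remaining |
|---|---|---|---|
| 3 | 0.47 | 11.8 | 13.2 |
| 5 | 0.32 | 7.9 | 17.1 |
| 7.4 | 0.23 | 5.7 | 19.3 |

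**3. False positives with a week-12 change.** The simulation used n = 25, 2000 trials per cell and a Cox likelihood-ratio test from enrolment. The marker has no predictive value. Its log change is N(0, SD), plus a fixed rise if the patient has progressed by the visit. OS is PFS plus an exponential residual with median 14.9 − m. Progression is recorded when it occurs. Entries are for percent change as a continuous covariate.

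| Assumptions | Living progressors sampled | At 0.05 | At 0.002 |
|---|---|---|---|
| m = 3, rise 0.4, SD 0.35 | all / half / a quarter | 51 / 31 / 18% | 10.2 / 5.0 / 1.8% |
| m = 7.4, rise 0.2, SD 0.5 | all / half / a quarter | 9.4 / 7.2 / 7.5% | 0.7 / 0.8 / 0.4% |
| No rise | all | 5–7% | – |

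Independent re-runs gave 48 / 32 / 19% for the first row and 9 / 7 / 7% for the second at 0.05. Simulation error near 7% is about √(0.07 × 0.93 / 2000) = 0.6 points, so the second row's half and quarter entries cannot be told apart from each other and barely from no effect. For the ±30% category the ranges at 0.05 were 7–36% (all sampled) and 6–20% (half).

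**4. A second simulation with other assumptions.** Here the marker is standard normal and shifts by 1 SD at progression, all progressors are sampled, and a Cox score test is used with 6000 runs. At assumed medians of 4 / 6 / 9 months, false positives at 0.05 were 34 / 24 / 18% with a week-12 change and 43 / 39 / 31% with a week-24 change. With zero shift they were 5–6%, so the inflation comes from the post-progression values.

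**5. Excluding patients progressed by the visit.** At week 12 the rate at 0.05 returns to 5–7% in both simulations. Restarting the clock makes no difference to the Cox fit when the visit is at the same study time for everyone: no included patient can have an event before it, so the risk sets are the same.

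**6. Late recording.** If half of progressions are recorded only on the week-24 scan, the unrestricted rates are 8–33% (all sampled) and 6–26% (half). Exclusion then gives 4–7%, or up to 12% if the marker picks up progression not yet recorded.

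**7. OS.** No sample follows death. By the argument in step 5, one common visit gives the same fit as a landmark; the simulated rate is 5–7%. With the last available change it is 5.5–6.4% under no or mild drift in the marker, and about 9% only under strong assumed drift.

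**The case against.** The primary analysis is for OS, and a reader might infer that it shares the bias. It does not, provided one common visit supplies the change. That stands.

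Fixed-covariate entry is an inference, and a plan for similar analyses leaves an analyst free to drop post-progression values. True, but nothing in the plan asks for it, and Section 10.1 keeps such patients evaluable.

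The findings are labelled preliminary, the time-varying model respects time order (if values are updated at their sampling dates and follow-up ends at progression), and the displays set markers beside progression events. All of this limits the harm. None of it corrects the two change models.

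The size is unknown. A reader might take the 50% figure as the expected error. It needs a short PFS, a strong marker reaction and every living progressor sampled, while Section 6 stops study drug when certain other treatments are given. At the mild end the inflation is close to nil. That stands.

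A reader might also infer that week-24 changes can never support a PFS model, because the Section 7.2 table schedules only survival follow-up afterwards. The documents do not support so firm a statement. Section 10.2 censors at the last evaluation with no week-24 limit, and the survival analyses may run until two years after the last patient completes treatment.

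The disagreement between Sections 3 and 7.2 on blood sampling is a separate point. It matters here only because a week-12 rule needs week-12 blood.

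**Conclusion.** The point holds for the PFS repeats of two of the four marker models. As written, they allow a covariate measured at or after the event, so a marker that only reacts to progression can appear to predict it. The direction is firm for any such marker. The size rests wholly on an assumed PFS median, marker rise, marker spread and share of progressors sampled: for a week-12 sample, from about 7% to about 50% at nominal 5%, against about 6% once patients progressed by the visit are excluded. The OS models need only a named common visit, and the baseline and time-varying models can stay as they are. This is a secondary, exploratory analysis, but the gap is more than missing detail, because following the text can produce the error.

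**What to change.** In Section 10.6, add:

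> For the PFS percent-change and ±30% models, change is taken at a named visit (week 12); only patients alive, progression-free and with a value at that visit are included, and no marker value taken at or after progression is used; Kaplan-Meier curves by change group start at that visit.

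Week 12 suits because marrow is taken then and the 4-weekly PSA and the week-24 scan follow it. Week-24 change may be used the same way, as a week-24 landmark, only if progression evaluations continue after week 24; otherwise report it descriptively. In Section 10.5, take change for OS at the same named visit for all patients. Reconcile the blood sampling times in Sections 3 and 7.2.

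The cost is SAP wording and precision. About 6 to 12 of 25 patients leave the PFS change models at assumed medians of 7.4 to 3 months, leaving 13 to 19. If all of those are followed to progression, the HR detectable with 80% power at two-sided 5% is exp(2.80/√events) = 1.9 to 2.2 per SD, against 1.76 with 25 events. If only the 4 to 6 events expected between weeks 12 and 24 are seen, it is about 3.1 to 3.8. The result describes progression after the named visit only. Progression present but not yet recorded then can still leave some bias. The OS change models lose any patient who misses week 12 but has a later sample.

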- To estimate the overall survival in patients with CRPC

3. Study design

This is an open label study to determine the effect of Alpharadin on the bone marrow microenvironment in patients with CRPC and bone metastases. We will determine the modulation of bone microenvironment as measured by serum, plasma, urine and bone marrow aspirate bone markers. The baseline determination and subsequent assessment of bone-prostate cancer paracrine signaling will be correlated with PSA decline, progression free survival, overall survival and changes in pain indices.

Subjects will be treated with the standard dosing of xofigo (Alpharadin) Ra-223 dichloride 50 kBq (0.0014 mCi)/kg intravenously every 4 weeks for 6 cycles (6 doses total).

For pharmacodynamic effects: tumor/osteoblast/osteoclast along with Ki-67 (proliferation marker), gamma H2AX (DNA double strand breaks), and cleaved PARP. Co-localization by immunohistochemistry for cytokeratin/PSA for tumor cells, BALP for osteoblasts, and TRAP staining for osteoclasts on bone marrow core samples. This will be performed at pre-treatment, week 12 and week 24.

For plasma markers (peripheral blood) indicative of bone formation and degradation this panel will be performed at baseline, week 12, week 16 and week 24: ALP (alkaline phosphatase) BALP* (bone alkaline phosphatase), OPG (osteoprotegerin), RANKL (receptor activator of nuclear factor-B ligand), OPN (osteopontin), OC (osteocalcin), CTX (c-telopeptide-collagen), PINP* (n-terminal propeptide of type 1 procollagen),

Bone secreted factors in the bone marrow aspirate that reflect the status of osteoblasts or osteocytes

1. Alkaline phosphatase--osteoblasts
2. Osteocalcin—both osteoblasts and osteocytes
3. DMP (Dentin matrix acidic phosphoprotein 1)
4. Sclerostin markers of osteocytes

Bone secreted factors that modulate tumor cell activity and tumor cell response to therapies

1. Tenascin—activate integrins
2. Periostin—activate integrins
3. Lumican—active integrins
4. Decorin—binding to EGFR, IGFR, MET, class A scavenger receptor (SR-A)
5. Osteopontin-binding to CD44 and integrins
6. Osteonectin—activate integrins
7. Nidogen-1—activate integrins
8. TGFb-induced protein ig-h3—activate integrins

Urine: NTx (n-terminus cross-linking telopeptide) a marker of osteoclast activity.

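### Percent change and the ±30% classes are set for every marker, but they break down for markers that can be zero at baseline and have no meaning for ordinal ones

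*Combined protocol and SAP*

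**What the plan says.** Section 10.5 plans four Cox analyses per marker for overall survival: the baseline value, the percent change, a three-level change category, and all observed values as a time-varying covariate. On scale it says "Markers measured on a continuous or ordinal scale will be included with their original units in the model". For the second analysis it says "Next we will calculate the percent change from baseline and use that as a continuous measure in the model", and for the third "The ordered category of reduced by 30%, same, or increased by 30% grouping will be used in the model".

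The bands come from 10.4: "Patients will also be classified for each marker based on whether the marker decreased by at least 30%, stayed with 30% of baseline", or rose by the same margin. Section 10.3 adds a descriptive summary: "The proportions of patients with at least a 30% increase or decrease in any marker will be presented". Section 10.6 repeats the approach for progression-free survival.

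The scope is every marker. Section 10.4 treats the pharmacodynamic, serum and bone marrow markers together. Section 10.2 lists the pharmacodynamic group as "Tumor/osteoblast/osteoclast, Ki-67, gamma H2AX, cleaved PRP, cytokeratin/PSA, BALP, and TRAP". Section 3 describes these as stains on marrow core samples and includes "gamma H2AX (DNA double strand breaks), and cleaved PARP" (PRP in 10.2 is presumably the same marker). Neither section says how a stain is read: percent of cells positive, a short intensity score, a composite score or a count. Sections 10.3 to 10.5 give no rule for a zero baseline.

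**The concern.** Percent change suits quantities with a true zero that are reliably above it, such as alkaline phosphatase, CTX or PINP concentrations. Two kinds of marker do not fit.

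The first is any marker that can be zero before treatment. Gamma H2AX is stained as a measure of double-strand breaks, which section 1.4 gives as the drug's mechanism. Moving from absent to present is therefore a result the assay is meant to show, yet it has no percent change. Cytokeratin/PSA can also be absent, because eligibility in 4.1 rests on imaging and does not require tumour in the sampled core.

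The second is any ordinal marker. Dividing one rank label by another gives a number that depends mainly on where the patient started.

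The primary objective is to identify markers, including those in marrow biopsies. If the rule has no value for some patients, the analyst must drop them or choose an offset after seeing the data. Dropping them selects on the baseline value, and an offset can decide the result in a study of 25.

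**Working it through.** **1. The plan's own figures.** The documents give no figure on zero baselines or short scores. The nearest stated figure is the power in 10.8. For a continuous covariate in a Cox model, events = (1.960 + 0.842)² / (SD² × ln(HR)²).

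- HR 1.57, SD 1.25: 7.849 / (1.5625 × 0.2035) = 24.7 events; power with 25 events is 80.5%.
- HR 1.45, SD 1.5: 7.849 / (2.25 × 0.1381) = 25.3 events; power with 25 events is 79.6%.

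Both reproduce if all 25 patients count as events. The point below does not alter them.

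**2. Markers in scope.** Section 10.2 lists 7 pharmacodynamic, 8 serum and 12 bone marrow items, 27 in all. The tissue stains are 7 of 27, about a quarter.

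**3. Zero baseline.** Percent change = 100 × (follow-up − baseline) / baseline.

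- Baseline 0: the divisor is zero, so the continuous covariate does not exist, whatever the follow-up value.
- If the class is derived from that percentage, it does not exist either.
- If the class is read as a ratio rule (follow-up ≥ 1.3 × baseline, or ≤ 0.7 × baseline), 0 to any positive value is an increase. But 0 to 0 satisfies both 0 ≥ 0 and 0 ≤ 0, so the patient falls in both outer classes.
- If an offset is added after the fact, 0 to 2 becomes (2.1 − 0.1) / 0.1 = +2000% with offset 0.1, and (3 − 1) / 1 = +200% with offset 1.

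**4. Ordinal score (length assumed).** One-step moves from a non-zero baseline that reach 30%:

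| Score | Moves | At least 30% |
|---|---|---|
| 0–2 | 3 | 3 |
| 0–3 | 5 | 5 |
| 0–4 | 7 | 6 |
| 0–5 | 9 | 6 |
| 0–8 | 15 | 6 |
| 0–12 | 23 | 6 |

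On 0–3 the moves are 1→0 −100%, 1→2 +100%, 2→1 −50%, 2→3 +50% and 3→2 −33.3%. On 0–4 the exception is 4→3, −25%.

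**5. Percent-positive cells (read-out assumed).** A move from 1% to 2% is +100%, an increase; 40% to 50% is +25%, no change. A baseline above 100 / 1.3 = 76.9% can never reach the increased class.

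**6. Illustration of loss.** Suppose that zero-baseline patients were dropped from the percent-change model, that all the others were evaluable and died, and that HR 1.57 with SD 1.25 applied. Power = Φ(√events × 1.25 × ln 1.57 − 1.960).

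| Assumed zero-baseline share | Events | Power |
|---|---|---|
| 0% | 25 | 80% |
| 10% | 22.5 | 76% |
| 20% | 20 | 71% |
| 30% | 17.5 | 65% |
| 40% | 15 | 59% |

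The shares are assumptions; the documents give none.

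**The case against.** The best case for the plan has four parts.

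*The read-out is unknown.* No stain is identified as ordinal or percent-positive, and the sentence on scales in 10.5 is generic. Appendix 1 (biopsy) and Appendix E (correlative work) are cited but are not in the text reviewed, so a scoring rule may stand there. This stands: the score examples are illustrations only. It does not remove the fault, because 10.5 itself allows ordinal markers and then prescribes percent change without exception.

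*The class needs no division.* On the ratio reading, absent-to-present counts as an increase. That is right, and it means one cannot say the signal is necessarily lost from the class. It leaves the continuous model undefined and 0 to 0 in two classes.

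*Other analyses cover the gap.* The baseline and time-varying models do not divide by baseline, and 10.4 speaks broadly of changes as continuous measures. This also stands, but it does not repair the two change analyses that 10.5 specifies.

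*The work is exploratory.* Section 10.8 says so, but also says the findings will be used to design later trials. An undefined covariate is a fault in either setting.

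A reader might infer more than the documents support:

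- That any one-step change counts as a 30% change, or that the middle class shrinks to exact ties. Both hold only for scores with a maximum of 3 or less and a non-zero baseline.
- That the classes denote response or progression. The plan uses only decreased, unchanged and increased.
- That zero-baseline patients are excluded. Section 10.4 includes anyone with a baseline and a later value, and names no such exclusion.
- That a set number of the 25 would be lost. The zero-baseline share is unknown, and under 10.1 only patients with usable biopsies before and after treatment are evaluable for marrow markers.

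**Conclusion.** The concern holds in a limited form. The plan sets one change rule for all markers. For any marker that can be zero at baseline, that rule gives no value in the continuous model and no clear class in the categorical one. For any ordinal marker it gives a figure with no stable meaning.

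For each such marker the reach is two of four Cox analyses for overall survival, their repeats for progression-free survival, and the 30% summary in 10.3. How many markers and patients are affected cannot be determined from the documents; it depends on how the seven pharmacodynamic stains are read and how often they are absent before treatment. The sample size, the stated power and the baseline and time-varying models are untouched. The point is worth correcting before marker data are analysed, but it does not undermine the design.

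**What to change.** In 10.4 and 10.5:

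- Keep percent change and the ±30% bands for serum, plasma, urine and marrow-aspirate concentrations.
- State the read-out of each tissue stain, or point to the appendix that gives it.
- For tissue markers that are ordinal or can be zero, use absolute change: step change for ordinal scores, percentage-point change for percent-positive cells.
- For those markers, replace the ±30% class with decreased, same or increased. For percent-positive read-outs, fix the margin for *same* in advance; without one, a single-point move would count as a change.
- State that patients with a zero baseline stay in both change analyses.

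The summary in 10.3 and the repeats in 10.6 then follow the same split. The cost is a few sentences, with no change to sample size or procedures. The small downside is that tissue and fluid markers are reported on different change scales.

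### The Cox models for marker change leave out the marker's own baseline, and no marker Cox model includes extent of bone disease, so the plan cannot show what change, or the marker itself, adds

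*Combined protocol and SAP*

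**What the plan says.** Section 10.5 sets the form of the analysis: "Each marker will be tested individually using a Cox regression model to determine whether it is associated with overall survival". Four versions follow for each marker.

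- Baseline: "First, the baseline values will be used to determine if the baseline is associated with survival".
- Percent change: "Next we will calculate the percent change from baseline and use that as a continuous measure in the model".
- Category: "The ordered category of reduced by 30%, same, or increased by 30% grouping will be used in the model".
- Time-varying: "all observed values of the marker will be included as a time-varying covariate in the Cox regression model".

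No version names a second covariate. Baseline has its own model and is not carried into the percent-change or category models. Section 10.6 applies similar analyses to PFS.

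Section 10.2 lists the demographic variables as "Age at enrollment, race, ethnicity, ECOG status, extent of bone disease", the last in three levels (<6, 6-20, >20). They meet the markers in one place only, the regression-tree partitioning that section 10.5 makes optional: "Cutpoints will be examined together with demographic and medical status variables".

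For publication, section 10.5 calls a marker meaningful at p ≤ 0.002. For planning future trials it applies no multiplicity adjustment.

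**The concern.** Two separate problems follow from the one-covariate form.

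**Change without baseline.** High values tend to fall more, so percent change is usually negatively correlated with the starting value. If the starting value is prognostic, a model with change alone attributes part of that effect to change. A change with no effect of its own can then look associated with survival. If higher baseline and rising values both raise the hazard, the two effects partly cancel and a real effect of change is masked.

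**Marker without disease extent.** Bone markers may reflect how much bone disease is present. A marker that only tracks extent, and carries no information beyond it, can look prognostic.

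The primary objective (section 2) is to find markers of predictive and prognostic importance, and section 10.8 seeks markers that move under treatment and relate to survival. Whether on-treatment change tells more than the baseline value is close to the centre of that aim, and the specified models cannot answer it. Future trials could be built on change in a marker when only its baseline mattered, or on a marker that stands in for a lesion count already available.

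**Working it through.** **1. The plan's own power figure.** Section 10.8 gives 25 patients, 80% power, two-sided 5%, and HR 1.57 at SD 1.25 or HR 1.45 at SD 1.5. For one continuous Cox covariate, events needed = (1.960 + 0.842)² / [SD × ln(HR)]².

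- HR 1.57, SD 1.25: 24.7 events; power with 25 events is 80.5%.
- HR 1.45, SD 1.5: 25.3 events; power with 25 events is 79.6%.

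The figures reproduce for a model with no other covariate and a death in all 25 patients. Per SD, the detectable effect is 1.57^1.25 = 1.76 or 1.45^1.5 = 1.75.

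**2. Number of deaths.** The survival analysis is due at 90% deaths (0.90 × 25 = 22.5, so 23) or two years after the last patient completes treatment, whichever comes first. I take 20 deaths as an assumption and 23 as the value at the 90% trigger.

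**3. Change without baseline.** Simulated trials: 25 patients, exponential survival cut at the 20th death, baseline HR 1.75 per SD, change with no effect given baseline, likelihood-ratio test. The correlation r between change and baseline is assumed.

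| r | Change alone, 5% level | Baseline added, 5% level | Change alone, 0.002 level | Baseline added, 0.002 level |
|---|---|---|---|---|
| -0.3 | about 10% | 6-7% | about 0.6% | about 0.3% |
| -0.5 | about 20% | 6-7% | about 2.0% | about 0.3% |
| -0.7 | about 34% | 6-7% | about 5.5% | about 0.3% |

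With baseline HR 1.2 per SD, change alone gives 7-9% at the 5% level. With HR 1.0 it gives 5-6%, which is no inflation.

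**4. Which r is plausible?** For a simple difference with equal variances, r = -√[(1-ρ)/2], where ρ is the baseline/follow-up correlation. Hence ρ = 1 - 2r²: 0.82, 0.50 and 0.02 for the three rows. The last row is an extreme case. A second simulation formed percent change directly from log-normal values with ρ from 0.9 to 0.5 (23 deaths, Wald test). Change alone gave 6-9% at the 5% level for baseline HR 1.5 per SD, and 8-15% for HR 2.0. At 0.002 it gave at most 0.64%.

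**5. Marker without extent.** Assumed: 23 deaths, extent levels in proportions 20/40/40%, marker/extent correlation 0.3-0.7, marker with no effect given extent, Wald test.

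| HR per extent level | Marker alone, 5% level | Marker alone, 0.002 level |
|---|---|---|
| 1.5 | 7-16% | 0.2-0.9% |
| 2.0 | 9-32% | 0.3-3.5% |

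With extent in the model the rate is about 6% at the 5% level.

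**6. Effect of adding baseline on power.** Change HR 1.75 per SD, 20 deaths, 5% level.

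| r | Baseline not prognostic: change alone → baseline added | Baseline HR 1.75 per SD: change alone → baseline added |
|---|---|---|
| -0.3 | 62-63% → 59% | 31% → 59% |
| -0.5 | 63% → 52% | 19% → 51% |
| -0.7 | 62% → 38% | 11% → 40% |

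**The case against.** The strongest reply is that crude association is the stated question. Sections 10.5 and 10.8 ask whether a marker is associated with survival, promise no independent or incremental value, and call all findings preliminary. The baseline model is fitted first, so baseline and change results can be read side by side. This stands as a reason to keep the unadjusted models. It does not remove the gap: two separate one-covariate results do not show whether change adds to baseline.

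The size is also open to challenge. The documents give no correlations and no baseline or extent effects, and section 10.4 says it is not known how these markers predict survival. The 34% figure needs a marker whose follow-up value is almost unrelated to baseline, and at 0.002 the absolute rates are much lower. All of this stands. However, the 0.002 bar deals with the number of markers (0.05/25), not confounding, and it does not govern selection for future trials.

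Finally, adjustment costs power in a 25-patient study. That stands where baseline is not prognostic; where it is, adjusting can raise power.

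Two stronger readings are tempting. A reader might infer that the plan ignores disease extent altogether. It does not: the optional cutpoint work examines demographic variables, extent among them, though that leaves the Cox tests unadjusted. A reader might also infer that omitting baseline promotes markers unrelated to survival. It does not: the inflation requires a prognostic baseline, so the marker is truly associated with survival and only the credit given to its change is in doubt.

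**Conclusion.** The concern holds in limited form. Every Cox model specified in section 10.5, and by extension 10.6, is univariable. The change models omit the marker's baseline, and no Cox model includes extent of bone disease. The plan therefore cannot show whether on-treatment change adds to baseline, or whether a marker is more than a proxy for disease extent.

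The size depends on unknowns. With a baseline effect as large as the one the plan is powered to detect, the false-positive rate for change roughly doubles at r = -0.3 and is about four times nominal at r = -0.5. It is close to nominal when the baseline effect is weak. The extent problem ranges from slight to substantial with the assumed correlation and effect. The unadjusted models remain valid as descriptions of crude association; the documents do not support calling them invalid. The change is worth making because the needed variables are already collected.

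**What to change.** In section 10.5, and correspondingly in 10.6 for PFS:

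1. Keep the planned unadjusted models and label them as crude associations.
2. Beside each percent-change and 30%-category model, report the same model with the marker's baseline value added. Base any statement that a change predicts survival on that second model.
3. Beside each marker's baseline-value model, report one supportive model with extent of bone disease as a single ordinal score.
4. Allow at most two covariates per model and use likelihood-ratio or Firth-penalised inference.
5. State as a limitation that a change model containing baseline still does not adjust for extent.

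The cost is a few lines of text and some extra models per marker, with no new data. Each adjusted model spends one more parameter on about 20-23 deaths. If baseline is not prognostic, the power loss is that shown in the last table of the working: small at a correlation of -0.3 and considerable at -0.7.
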